
Inclusion Criteria
	
 1. Meet the diagnostic criteria for refractory rheumatoid arthritis 2. Patients who have been treated with conventional disease-modifying rheumatic drugs and have been treated with 2 or more biologic/targeted disease-modifying anti-rheumatic drugs and require Abciap in combination with JAK inhibitors

Exclusion Criteria
	
 1. Those who do not meet the above inclusion criteria 2. Patients with tumors, hematological diseases and other autoimmune diseases 3. History of allergy to the drugs selected for this study 4. Patients who cannot adhere to the treatment of Abciap combined with JAK inhibitors, or who have serious adverse reactions and have not completed the observation course specified in the study

Research Progress Plan
	
2022.03-2024.03

Statistical analysis methods
	
SPSS software was used for statistical analysis. Normality tests were performed using SPSS software was used for statistical analysis. Normality tests

	
were performed using the Kolmogorov-Smirnov test, and measures conforming to a normal distribution were expressed as mean \pm standard deviation ($\bar{x} \pm s$), and comparisons between groups were made using the two independent samples t-test; measures not conforming to a normal distribution were described by median and interquartile spacing, i.e., median (25th percentile, 75th percentile) [M(P25,P75)], and comparisons between groups were made using the Mann-Whitney U anecdotal test The difference between groups was considered statistically significant at $P < 0.05$. The data were analyzed by the chi-square test or Fisher's exact probability method.

Form of publication of research results	Published 1-2 papers

1. Purpose of the study

(1) To observe the effect of Abasip combined with JAK inhibitor on the clinical efficacy of D2TRA patients

(2) To observe the safety of Abciap combined with JAK inhibitor in the treatment of D2TRA patients

2. Background of the study

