(3) Specific study: 90 D2TRA patients who were ineffective to conventional disease-modifying antirheumatic drugs and ineffective to treatment with 2 or more biological/targeted disease-modifying antirheumatic drugs and treated with Abacap combined with JAK inhibitors attending the outpatient and inpatient departments of Zhejiang Provincial People's Hospital from March 2022 to March 2024 were prospectively included as the observation group. Thirty patients with D2TRA treated with abciap alone in the outpatient and inpatient departments of Zhejiang Provincial People's Hospital from August 2020 to November 2021 were selected as the historical control group. There was no statistically significant difference between the observation group and the control group in terms of gender, age, disease duration, number of pressure pain in 28 joints, number of swelling in 28 joints, and DAS28 score ($P > 0.05$). Drugs were billed according to the maximum number of days of medical insurance (4 weeks), and changes in laboratory tests, number of pressure pains in 28 joints, number of swelling in 28 joints, and DAS28 score were observed in the Abciap combined with JAK inhibitor treatment group, and pre- and post-self comparisons were performed at 0, 4, 8, 12, 16, 20, and 24 weeks, along with changes in joint ultrasound and adverse effects. The changes in laboratory tests, number of pressure pains in 28 joints, number of swelling in 28 joints, and DAS28 scores were also retrospectively collected from the group treated with Abacap alone, and before and after self-comparison was performed at 0, 4, 8, 12, 16, 20, and 24 weeks, along with observation of changes in joint ultrasound and adverse effects. In addition, we observed the changes in laboratory tests, the number of pressure pains in 28 joints, the number of swelling in 28 joints, and the DAS28 score at 0, 4, 8, 12, 16, 20, and 24 weeks in the group treated with Abatacept combined with JAK inhibitor and the group treated with Abatacept alone, and compared them between the two groups for a statistically significant difference at $P < 0.05$. We also observed the changes in joint ultrasound and The changes of adverse reactions were also observed between the 2 groups.

5. Research Methodology:

Enrollment criteria (diagnostic criteria, inclusion criteria, exclusion criteria)

(1) Diagnostic criteria

The diagnostic criteria for D2TRA refer to the definition criteria proposed by EULAR 2021:

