1. Failure of ≥ 2 b/tsDMARDs (with different mechanisms of action) after failure of csDMARDs therapy (unless contraindicated) according to the European Rheumatology Consortium recommended treatment.
2. Presence of ≥ 1 of the following signs indicative of active/progressive disease.
 - a. At least moderate disease activity (based on validated composite metrics including

joint counts such as DAS28-ESR > 3.2 or CDAI > 10).

- b. Signs (including acute phase reactants and imaging) and/or symptoms (joint related or otherwise) suggestive of active disease.
 - c. Inability to taper glucocorticoid therapy (prednisone below 7.5 mg/day or equivalent dose).
 - d. Rapid progression of imaging (with or without signs of active disease).
 - e. Good control of the disease according to the above criteria, but still have RA symptoms that lead to a reduced quality of life.
3. Rheumatologists and/or patients who perceive signs and/or symptoms as problematic in the treatment.

All three criteria need to be present in D2T RA.

b, Biological; CDAI, clinical disease activity index; cs, conventional synthesis; DAS28-ESR, the disease activity score of 28 joints was evaluated by ESR; DMARD, disease-modifying antirheumatic drug; mg, milligram; RA, rheumatoid arthritis; ts, targeted synthetic.

* Unless restricted by access to treatment due to socioeconomic factors.

† If csDMARD treatment is contraindicated, failure of ≥ 2 b/tsDMARDs with different mechanisms of action is sufficient.

‡ Rapid radiographic progression: change in van der Heijde-modified Sharp score ≥ 5 points at 1 year.

(2) Exclusion Criteria

1. Those who do not meet the above inclusion criteria
2. Patients with tumors, hematological diseases and other autoimmune diseases
3. History of allergy to the drugs selected for this study
4. Patients who cannot adhere to the treatment of Abciap combined with JAK inhibitors, or who have serious adverse reactions and have not completed the observation course specified in the study

6. Test procedure

1. Subject management

Subject recruitment method: Direct recruitment during the clinical care process

2. Informed consent process: Subjects voluntarily joined the study and voluntarily signed the informed consent form.

7. Research Program

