
8. Start and end of the experiment

9.Data Security and Monitoring Program

(This paragraph cannot be deleted, if not, fill in none. According to the requirements of the Ministry of Health's Measures for Ethical Review of Biomedical Research Involving Human Beings (2016), all research projects are required to have a data security and monitoring plan, and this item is one of the criteria for the ethics committee to review the project, please describe it specifically according to the requirements.)

(1) Overview of data management methods

1.Data are traceable. All clinical trial data correspond to specific subjects and investigators, and all modifications to the data are recorded in detail to create a series of traceable verification traces.

2.Correctness of data. The correctness of data mainly includes the authenticity and accuracy of data, all clinical trial data reflect the actual situation of the study truthfully without any falsification, fiction and tampering; the accuracy is reflected in the verifiable data sources, i.e. CRF, study records and entered data should be consistent with the data obtained from the actual study.

3.Data completeness. Study data were collected completely for each subject, and missing data due to special reasons were stated as to why they were missing.

4.Logical reasonableness of the data. To determine whether the data are logically unreasonable from a clinical perspective.

5.Timeliness of data. The data are observed and completed in a timely manner at the specified time points in the clinical trial.

(2) Adverse events and serious adverse events are reported and collected.

Reporting principles: 1. Report only adverse events related to the study drug 2. Complete the Spontaneous Adverse Event Report Form for all related adverse events (serious and non-serious)

The following information should also be included to determine if the event is related, possibly related, or potentially related to the drug. Determination of event-drug relevance includes: 1. reasonable temporal sequence 2. dose-response relationship 3. pharmacology 4. discontinuation of dosing and/or positive re-dosing.

Classification of the severity of drug-related adverse events:

Mild	The symptoms do not alter the patient's normal function.
Moderate	The symptoms result in some degree of functional impairment, but are not damaging, uncomfortable, or embarrassing.
Severe	The symptoms are definitely detrimental to health, with significant

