functional impairment or incapacity.

3) Medical safety measures

1. Collect information, focus on prevention. Supervise the department to report the risk information of clinical medical research in a timely manner, so that the information monitoring is in place and the risk prevention is effective.

2. Early warning, timely disposal. The department strengthens the monitoring of risks, regularly monitors and inspects, and once problems are found, reports them to the department head in a timely manner and takes decisive measures to control and resolve the risks in a timely manner, prevent the expansion and spread of risks, and minimize them.

3. We regularly assess risks and propose corrective measures to prevent them.

4. Before clinical research begins, the investigator must provide the subject with information about the treatment and the subject's rights and obligations, so that the subject fully understands and agrees to it, and signs an "informed consent" before the clinical research experiment can begin.

If one of the following situations occurs, the emergency handling procedures should be started immediately to stop the scientific clinical medical research and report to the Science and Education Section.

1. The research clinical medical research in the technical staff or key equipment, facilities and other auxiliary conditions change, can not properly carry out clinical research or may bring uncertain consequences.

2. The occurrence of serious adverse consequences directly related to the research clinical medical study.

3. The ethical flaws in this research-based clinical medical study.

4. The medical quality and medical safety risks associated with this research-based clinical medical study.

5. The clinical application of this research-based clinical medical study is inexact.

4) Communication with ethics committee and higher pharmacovigilance department

1. The research protocol needs to be developed and submitted to the Medical Ethics Committee for approval prior to the start of the project.

2. The project research should be filed with the higher drug regulatory authorities in a timely manner, and actively accept the guidance and supervision of the higher drug regulatory authorities.

5) Internal analysis plan for data

1. Data Collection

Information about patients who met the enrollment criteria and data from laboratory-related tests

were collected.

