①Case collection form: includes basic information of enrolled patients, related diseases, disease duration, treatment, and test data of related indicators for individual data analysis.

②Summary table: includes the patient's disease and related index examination data for overall data analysis.

2. Assessing the overall data situation

①Evaluate the integrity of each data source: timely recording of patient-related data to ensure data integrity.

②Evaluate the accuracy and consistency of aggregated data: randomly check whether the extracted data are consistent with those in the database to ensure data accuracy.

3. Data cleaning and collation

①Check for errors and outliers in the data that clearly defy common sense, and when found, first check that the same patient metadata are the same, then check how this data was collected, and finally how to assess whether it is an outlier from a technical point of view, by using relevant statistical indicators and methods such as setting upper and lower limits to deal with outliers.

②For special numbers, first mark "missing value", there is a perfect data dictionary to query the actual situation of this field, if not need to promptly communicate to confirm such issues

4. Data Collation

①Uniform formatting and naming rules for data

②Recoding of certain information to meet subsequent analysis needs

5. Data Visualization

Histograms, line graphs, scatter plots or heat maps are used to visualize the data of patient-related indicators to show the data results and trends more clearly, so that the study results can be presented more clearly.

6. Data Analysis

Complete the data and perform statistical analysis on those that meet the criteria

1) Frequency of data security and monitoring reports submitted to the ethics committee

The research in this project is a low-risk study, so an annual review frequency is used. Also, the principal investigator holds regular study meetings and notifies the ethics committee if there are changes in the risk/benefit ratio of the study.

10. Respect for ethical principles and related regulations

The study was conducted in strict compliance with international and domestic standards and norms,

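### Exclusion criterion 4 removes patients who have a serious adverse reaction and do not finish observation, which conflicts with the study's own safety purpose

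*Protocol*

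**What the plan says.** The Program Summary and section 5 (2) give the same exclusion criterion 4. It has two limbs. The first excludes patients who cannot adhere to abatacept plus a JAK inhibitor. The second adds: "or who have serious adverse reactions and have not completed the observation course specified in the study". The observation course runs from week 0 to week 24 (sections 4 (3) and 7).

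The link to the analysis runs through three places:

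- The section 5 heading lists exclusion criteria as part of the enrolment criteria.
- Section 9, item 5) 1, collects "Information about patients who met the enrollment criteria" together with their laboratory data.
- Section 9, item 5) 6, says: "Complete the data and perform statistical analysis on those that meet the criteria".

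Other parts of the protocol depend on these same patients:

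- Section 1 (2) gives as a purpose: "To observe the safety of Abciap combined with JAK inhibitor in the treatment of D2TRA patients".
- Section 4 (3) plans a comparison of groups: "The changes of adverse reactions were also observed between the 2 groups".
- Section 9 (2) requires a report form for every related event, whether serious or not.
- Section 9 (1), item 3, asks for complete data on each subject, with a stated reason where data are missing.
- The form in section 14 has a field for withdrawal because of the event.

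**The concern.** An eligibility criterion must be decidable before a patient enters. The second limb of criterion 4 cannot be: it needs a reaction to treatment and a failure to finish this study's own follow-up. A history of earlier reactions is not a possible reading, because the limb refers to the course specified in this study. The first limb could be a screening judgement, but nothing in the text prevents its use after treatment has begun.

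Three results are at stake.

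- **Safety.** The rate of serious reactions in the analysed group is understated, and the rate of serious reactions with non-completion becomes zero by construction.
- **Before-and-after efficacy.** The comparison moves toward completers, who will look better if patients who leave early do worse.
- **Combination against historical control.** The first limb names only the combination, so how criterion 4 applies to the 30 controls is undefined. The direction of any bias depends on how it is applied and on which group has more non-completion.

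**Working it through.** The protocol gives no event rate, dropout rate, standard deviation or effect size, and no derivation of the 90, so there is no stated figure to reproduce. The finding rests on the text. The numbers below only show scale. From the document come 90 combination patients, 30 controls and P < 0.05; every other input is an assumption.

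**Text.** Take a patient who starts the combination, has a serious reaction at week 6 and leaves.

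1. Criterion 4 excludes this patient.
2. Under the section 5 heading, the patient therefore does not meet the enrolment criteria.
3. Section 9, items 5) 1 and 5) 6, then leave the patient out of the collected and analysed group.
4. Section 9 (2) and the section 14 form still allow the individual event to be recorded.
5. No section puts the patient back into a denominator or into the group comparison.

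A patient with a serious reaction who completes observation is not caught. Leaving for lack of efficacy is not named.

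**Safety.** Assume 12 of 90 treated patients have a serious reaction, and k of those 12 do not complete and are removed. The analysed rate is (12 − k)/(90 − k).

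| k removed | Analysed rate | Exact 95% CI |
|---|---|---|
| 0 | 12/90 = 13.3% | 7.1–22.1% |
| 3 | 9/87 = 10.3% | |
| 6 | 6/84 = 7.1% | |
| 9 | 3/81 = 3.7% | 0.8–10.4% |
| 12 | 0/78 = 0% | |

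**Before-and-after efficacy.** Overstatement of mean DAS28 improvement = proportion removed × deficit of non-completers. Assume a deficit of 1.0 to 1.5 points.

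- 10% removed (81 analysed): 0.10–0.15 points
- 20% removed (72 analysed): 0.20–0.30 points
- 30% removed (63 analysed): 0.30–0.45 points

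For remission, assume 40% in completers and 5% in non-completers. The rate in all treated patients is (1 − p) × 0.40 + p × 0.05. This gives 36.5%, 33.0% and 29.5% at p = 10%, 20% and 30%, and each would be reported as 40%.

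**Between groups.** Simulation with 20,000 replicates per scenario, 90 against 30 starters, no true difference among all starters, non-completers 1.0 or 1.5 points worse, SD 1.2 (taken within subgroups or in total), pooled t-test.

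| Scenario | Mean false difference | False-positive rate |
|---|---|---|
| Both groups filtered, equal non-completion | about 0 | about 5% |
| Combination only filtered, 10% removed | 0.10–0.15 toward combination | 7–10% |
| Combination only filtered, 20% removed | 0.20–0.30 toward combination | 12–25% |
| Combination only filtered, 30% removed | 0.30–0.45 toward combination | 20–47% |
| Both filtered, 20% combination, 10% control | 0.10–0.15 toward combination | 6.5–10% |
| Both filtered, 10% combination, 20% control | 0.10–0.15 against combination | 6–8% |

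The second limb alone cannot remove more patients than have serious reactions. With 12 of 90 that ceiling is 13.3%, so the 20% and 30% rows also need the adherence limb to be used after treatment has started. With exactly 12 of 90 removed from the combination group only (SD 1.2 within subgroups), the false-positive rate is about 7–11%.

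**The case against.** The strongest reply is that the step from exclusion criterion to analysed group is an inference. The sentence in section 9, item 5) 6, does not say which criteria it means, and it follows text on data checks and outliers, so it could refer to data quality. Section 11 names tests and defines no completer set. Sections 4 (3) and 7 describe the observation group as patients treated with the combination, with no condition on completion. The completeness rule in section 9 (1) suggests keeping incomplete patients and explaining the gaps. Individual events can still be reported, and analysis sets are commonly left to a SAP, which may exist.

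Part of this stands. The wording of item 5) 6 is loose, event recording survives, and the absence of a defined safety set would not by itself be a finding. It does not remove the problem. The complaint is about a rule the protocol states, and a SAP could keep these patients only by overriding criterion 4. The completeness rule adds to the contradiction, since it treats non-completion as something to explain while criterion 4 treats it as a reason for removal.

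The objection to the efficacy sizes is also partly right. The 1.0–1.5 point deficit is assumed. If patients who stop for toxicity have no DAS28 deficit, the false-positive rate stays near 5%; with only 2 to 6 patients removed it is about 5–6%. The safety understatement depends on none of this.

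**Conclusion.** The concern holds and must be fixed. Criterion 4 mixes eligibility with a post-treatment outcome. Followed as written, it takes out of the analysed group exactly the patients that the safety purpose, the adverse event form and the planned group comparison are meant to describe.

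Confidence is high on the wording, and on the direction of the safety error whenever any patient meets the second limb. The sizes are illustrative: a serious reaction rate of 13.3% could be reported as anything from 10.3% down to 0% as 3 to 12 of the 12 affected patients are removed. Efficacy overstatement depends on non-completers doing worse. The between-group comparison favours the combination only if that group alone is filtered or has more non-completion; with less non-completion in that group the bias reverses. The protocol does not settle which case applies.

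**What to change.** 1. In the Program Summary and in section 5 (2), limit criterion 4 to conditions known before the first combined dose, and delete the limb on serious reactions with uncompleted observation.
2. Add one sentence on who is analysed: every eligible patient who received at least one dose enters the safety analysis and the main efficacy analysis, using the visits available.
3. Apply the same rule to the 30 historical controls.
4. Report the number of non-completers and their reasons in each group, and show completers only as a sensitivity analysis.

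Counting non-completers as not in remission is a reasonable option for the DAS28 categories, but the fix does not depend on it.

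The cost is a wording amendment in two places plus one sentence, submitted to the ethics committee as section 10 requires. No new patients or procedures are needed. The real work is checking control charts for patients who started abatacept and stopped early, which could change who the 30 controls are. Reported efficacy and safety may look slightly less favourable. None of this changes how patients are treated.

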However, there are some patients whose disease activity is still not effectively controlled. Therefore, according to the 2021 European League Against Rheumatism (EULAR) recommendations, RA is defined as refractory RA (difficult-to-treat rheumatoid arthritis, D2TRA) when the following three criteria are met: (1) failure of csDMARDs after treatment according to the EULAR recommendations (unless there is a contraindication) after failure of ≥ 2 tsDMARDs (with a different mechanism of action); (2) presence of at least one of the following: at least moderate disease activity; signs and/or symptoms suggestive of active disease; inability to taper glucocorticoid therapy; rapid imaging

progression; RA symptoms leading to decreased quality of life; (3) rheumatologists and/or patients who believe that signs and/or symptoms of treatment is problematic.

Due to the complex etiology and pathogenesis of D2TRA, poor treatment outcomes, insufficient clinical attention and focus, high rates of bone erosion and even joint deformity. In addition, the high incidence of D2TRA is mostly in middle age, which is at the peak of career and belongs to the main group of social work. Once the disability is caused by "failure to treat", it will not only cause the patients' physical function, quality of life and social participation to decrease, but also bring a huge economic burden to the patients' families and society. It is no less harmful than some lethal diseases and other geriatric diseases.

Therefore, it has become an important task in the field of rheumatology and immunology to explore and find new methods and means to treat D2TRA. In the last decade, a variety of novel bDMARDs (e.g., abciap) and tsDMARDs (e.g., JAK inhibitors) have been introduced, all of which have demonstrated fruitful anti-inflammatory and disease activity improvement in the treatment of RA patients. Studies have shown that in patients with RA who are poorly treated with methotrexate or tumor necrosis factor inhibitors, treatment with Abciap (ABT) in combination with methotrexate has been shown to improve joint symptoms, reduce disease activity, slow the deterioration of damaged joint structures and improve physical function.

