The 2019 European League Against Rheumatism (EULAR) has updated its recommendations for the management of RA in conjunction with the latest research findings in the field. Provides guidance on drug combinations for the treatment of RA. It is considered that when response is still inadequate after 3-6 months of conventional treatment with methotrexate and glucocorticoids, patients should be stratified according to their own risk factors to guide treatment. That is, if poor prognostic factors are present (presence of autoantibodies, high disease activity, early onset of erosion, or failure of both csDMARDs treatments) bDMARDs or JAK inhibitors in combination with csDMARDs should be

added. If this fails, other bDMARDs or tsDMARDs are recommended. Abbasi M et al. comprehensively explored the development of new and recent treatment regimens for RA by combining conventional, newly developed, and still-in-study RA treatment strategies and proposed that the use of biologics or biosimilars alone, or in combination with DMARDs, can further improve RA and is a better treatment options. Therefore, in the face of D2TRA and poor treatment with traditional DMARDs, the use of novel immunosuppressive agents alone or in combination with two immunosuppressive agents is a new therapeutic direction that can be sought.

3. Test basis

(1) Pre-study animal experiments and literature base

Animal experiments: Iglesias M et al. A short course of tofacitinib sustains the immunoregulatory effect of CTLA4-Ig in the presence of inflammatory cytokines and promotes long-term survival of murine cardiac allografts. This study from the United States showed that JAK inhibitors combined with CTLA4-Ig in the presence of inflammatory cytokines maintained the immunomodulatory effects of CTLA4-Ig and promoted long-term survival of murine cardiac allografts. Literature Base: EULAR recommendations for the management of rheumatoid arthritis with synthetic and biological disease-modifying antirheumatic drugs: 2019 update.

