No intervention factors were imposed on the study subjects in the study. Prospectively, 90 patients with D2TRA who were ineffective to conventional disease-modifying antirheumatic drugs and ineffective to treatment with 2 or more biological/targeted disease-modifying antirheumatic drugs and treated with Abacap combined with JAK inhibitors attending the outpatient and inpatient departments of Zhejiang Provincial People's Hospital from March 2022 to March 2024 were included as the observation group. Thirty patients with D2TRA treated with abciap alone in the outpatient and inpatient departments of Zhejiang Provincial People's Hospital from August 2020 to November 2021 were selected as the historical control group. There was no statistically significant difference between the observation group and the control group in terms of gender, age, disease duration, number of pressure pain in 28 joints, number of swelling in 28 joints, and DAS28 score ($P > 0.05$). The dosage was 125 mg per dose by subcutaneous injection once a week, and the dosage was 5 mg per dose by oral injection twice a day. The drug was billed according to the maximum number of days of medical insurance (4 weeks), and patients were observed for rheumatoid factor, anti-cyclic citrullinated peptide antibodies, immunoglobulins (IgG, IgA and IgM), C-reactive protein, blood sedimentation, white blood cells, platelets, ghrelin, glutamic aminotransferase, glutamic oxalacetic aminotransferase, globulin, creatinine, glomerular filtration rate, 28 joints at 4, 8, 12, 16, 20 and 24 weeks before and after drug administration number of pressure pain, number of swelling in 28 joints, joint ultrasound, change in DAS28-ESR score and adverse effects. To observe the changes in laboratory test indices, number of pressure pain in 28 joints, number of swelling in 28 joints, and DAS28 scores in the Abciap combined with JAK inhibitor treatment group, before and after self-comparison at 0, 4, 8, 12, 16, 20, and 24 weeks, as well as the changes in joint ultrasound and adverse effects. Also retrospectively collected the changes in laboratory test indices, number of pressure pain in 28 joints, number of swelling in 28 joints, and DAS28 score in the group treated with Abacap alone, and performed a before-and-after self-comparison at 0, 4, 8, 12, 16, 20, and 24 weeks, while observing the changes in joint ultrasound and adverse effects. In addition, we observed the changes in laboratory indices, the number of pressure pain in 28 joints, the number of swelling in 28 joints, and the DAS28 score between the Abciap and JAK inhibitor treatment groups at 0, 4, 8, 12, 16, 20, and 24 weeks, and compared them between the two groups. The changes in joint ultrasound and adverse effects between the two groups were also observed, so as to observe the clinical efficacy and safety of the Abciap combined with JAK inhibitor treatment group. $DAS28 \leq 2.6$ was defined as clinical remission, $2.6 < DAS28 \leq 3.2$ as low activity, $3.2 < DAS28 \leq 5.1$ as moderate activity, and $DAS28 > 5.1$ as high activity.

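### Abatacept *alone* is undefined for the historical controls, and csDMARD background is neither compared nor adjusted for, so a csDMARD difference between the cohorts could be credited to the JAK inhibitor

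*Protocol*

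**What the plan says.** The group definitions appear three times in the Protocol: in the Program Summary (research methodology), in section 4 (3) and in section 7. Controls are "Thirty patients with D2TRA treated with abciap alone", seen from August 2020 to November 2021. The observation group is 90 patients "treated with Abacap combined with JAK inhibitors attending the outpatient and inpatient departments", seen from March 2022 to March 2024.

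Section 7 also states "No intervention factors were imposed on the study subjects in the study", so background treatment follows routine care. The groups are declared not to differ "in terms of gender, age, disease duration, number of pressure pain in 28 joints, number of swelling in 28 joints, and DAS28 score". These are six variables, and csDMARD use is not one of them.

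The diagnostic criteria in section 5 require earlier csDMARD failure unless contraindicated. Neither they nor the exclusion criteria require csDMARDs to be stopped, kept stable or matched. The logging form in section 13 has no csDMARD line. The case collection form in section 9 (data collection) has a general treatment item.

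Section 11 compares groups by the independent-samples t-test or the Mann-Whitney test, with chi-square or Fisher's exact test for counts. No adjusted comparison is stated.

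**The concern.** The between-group comparison is there to show what a JAK inhibitor adds to abatacept. For that, the groups should be alike in other active antirheumatic treatment, or the analysis should account for the difference.

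The Protocol itself treats csDMARDs as active partners of these drugs. In section 2 it reports that "treatment with Abciap (ABT) in combination with methotrexate has been shown to improve joint symptoms, reduce disease activity", and it cites a recommendation that "bDMARDs or JAK inhibitors in combination with csDMARDs should be" added when poor prognostic factors are present.

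If csDMARD use differs between the cohorts, an unadjusted test cannot tell that difference from the JAK inhibitor's contribution. This is not only a detail left to a later analysis plan: the group definition belongs in the protocol, and section 11 already commits to unadjusted tests for a non-randomised comparison.

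**Working it through.** The Protocol gives no effect size, SD, power or csDMARD frequency, so there is no stated figure to reproduce. The check has two parts.

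**1. What *alone* can mean.**
- In all three definitions, *alone* is set against the combination with a JAK inhibitor. This points to *without a JAK inhibitor*.
- Section 2 uses the word in two ways. One sentence, on a cited review, says "the use of biologics or biosimilars alone, or in combination with DMARDs, can further improve RA"; there *alone* means without DMARDs. The next sentence contrasts one novel immunosuppressive agent with a pair of them; there *alone* means without a second novel agent.
- Section 2 also labels JAK inhibitors as tsDMARDs in one place and as csDMARDs in another, so the Protocol's own terms do not settle the question.

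Under the looser meaning, csDMARDs are unrestricted in both groups. Under the stricter meaning, they are absent in controls and unrestricted in the observation group. Neither meaning ensures equal use.

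**2. Scale, on assumed inputs.** Only the group sizes, 90 and 30, and the 0.05 level come from the Protocol; the test is taken as two-sided. Assumed: SD of DAS28 1.2 to 1.5, csDMARD effect 0.3 to 0.6 DAS28 points, no true JAK inhibitor effect.

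- Bias = (difference in share on a csDMARD) × (csDMARD effect).
- SE = SD × √(1/90 + 1/30): 1.2 × 0.2108 = 0.253; 1.5 × 0.2108 = 0.316.
- Rejection probability = Φ(−1.96 + bias/SE) + Φ(−1.96 − bias/SE).

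| Gap in csDMARD use | Effect | Bias | Rejection, SD 1.2 | Rejection, SD 1.5 |
|---|---|---|---|---|
| 0 points | any | 0 | 5% | 5% |
| 25 points | 0.3 | 0.075 | 6.0% | 5.6% |
| 50 points | 0.3 | 0.15 | 9.1% | 7.6% |
| 50 points | 0.6 | 0.30 | 22% | 16% |

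The table is symmetric. If more controls than combination patients take a csDMARD, the same probabilities apply with the sign reversed, and a real JAK inhibitor effect would be understated.

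**Cost of restriction.** Suppose controls prove to be csDMARD-free and 80% (assumed) of combination patients take one. Then 0.2 × 90 = 18 combination patients remain comparable. SE = 1.2 × √(1/18 + 1/30) = 0.358, against 0.253 with all 90. The difference detectable with 80% power, 2.80 × SE, rises from 0.71 to 1.00.

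**The case against.** A reader might infer that controls had to be free of csDMARDs, so that the trial compares JAK inhibitor plus csDMARD with neither. With no csDMARD use in controls, 50% to 80% use in the combination group, an effect of 0.3 to 0.6 and SD 1.2, the spurious difference would be 0.15 to 0.48 points and the false-positive rate about 9% to 48%. The documents do not support this as a finding. No section says controls were csDMARD-free, the wording more naturally contrasts with the JAK inhibitor combination, and nothing says controls had contraindications or had stopped csDMARDs.

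Three further objections have weight.
- The observation group is defined by earlier csDMARD failure, so the effect of a continued csDMARD may be small.
- A csDMARD continued from before week 0 is already partly reflected in week-0 DAS28, which is declared similar between groups. What remains is mainly treatment newly started or changed in one cohort, or a joint effect with abatacept.
- The cited recommendation and the methotrexate evidence concern earlier treatment stages, so they do not show that csDMARD use is common among these patients.

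These points rule out a claim about direction or size. They do not show that use is equal, and the Protocol has no step that would reveal or correct a difference. A covariate could be added in an analysis plan, but such a plan cannot establish what *alone* meant when controls were chosen.

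**Conclusion.** The concern holds as uncontrolled confounding by background treatment. *Alone* is undefined, csDMARD use is not restricted, compared or balanced in either group, and the stated tests are unadjusted. A csDMARD difference between two non-overlapping cohorts could therefore be attributed to the JAK inhibitor.

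Direction and size are unknown, and the bias is zero if use is equal. The 5% to 22% range is an illustration on assumed inputs, not an estimate. It treats the full csDMARD effect as falling after week 0 and so leans towards the larger side for csDMARDs continued from before. The missing definition alone would be a gap in detail; the case for change rests on a cheap adjustment that reduces confounding under either meaning.

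**What to change.** 1. In the Program Summary, section 4 (3) and section 7, state what *alone* meant when the controls were selected.
2. Extract week-0 csDMARD use (yes/no, and which drug) for both groups from the treatment item of the case collection form and the charts, and add it to the baseline comparison.
3. In section 11, replace the unadjusted DAS28 comparison with one adjusted for week-0 DAS28 and week-0 csDMARD use: ANCOVA, or a comparison stratified by csDMARD use.
4. If controls prove to be entirely csDMARD-free, there are no csDMARD-treated controls to compare with. Report the comparison restricted to csDMARD-free combination patients, and state that the overall difference cannot be attributed to the JAK inhibitor alone.

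The cost is chart extraction and some precision. The loss is substantial only if step 4 applies, as in the 18 against 30 example. A week-0 variable does not capture later csDMARD changes, so some confounding may remain. The changes concern description, recording and analysis; no rule on patients' background treatment is proposed.
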